#### 7.4. Study rationale

The evolution of treatments and management of patients with CML have made it a treatable chronic disease associated with possible functional cure. In the same capacity as choice of 1st line treatment, the choice of the treatment sequence should take into account previous lines of therapy, comorbidities and individual preferences.

In light of the availability of several targeted therapies for treatment of CP, AP or BC Ph+/CML, each with their own specific safety of use and tolerability profiles and their own concomitant mechanisms of resistance, it is important to evaluate the efficacy, safety, cross intolerance and current modalities for use (dose adjustment, temporary discontinuations, permanent discontinuations of treatment) of these treatments under real life conditions of use in France.

Adherence of patients to their treatment is essential in order to maintain the response to treatment. For the purpose of optimizing adherence to treatment, it is also important to evaluate the strategies used in clinical practice in terms of therapeutic management and management of adverse events related to treatment.

This study will make it possible to obtain data on the real-life conditions of use of bosutinib in treatment of CP, AP or BP Ph+/- CML, in patients previously treated with one or more TKIs and for whom imatinib, dasatinib and nilotinib are not considered as appropriate treatments.

This non-interventional study is designed as a PASS (Post-Authorization Safety Study) and it is conducted voluntarily by Pfizer.

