### **9.1. Study design**

This is a national, observational, descriptive, prospective, multicentre study conducted in metropolitan France in adult patients treated for accelerated or blast phase Philadelphia chromosome positive chronic myeloid leukemia, previously treated with one or more TKIs and for whom imatinib, nilotinib and dasatinib are not considered as appropriate treatments. The study will be conducted in all centres involved in management of CML, i.e. about twenty (20) in expected centres.

[figure not shown]
The study will be offered to the totality of patients who satisfy criteria for inclusion and for non-inclusion up to the end of the inclusion period defined as 4 years. About one hundred

(100) patients included are expected in the study. Therapeutic management of a patient will not be changed by participation in the study and will depend on decisions taken by doctors in agreement with current international recommendations (European Leukemia Net, ELN network [13]) (see paragraph 7.3).

Patients will be followed prospectively over a 3-year period starting with their inclusion in the study. The inclusion visit will be performed at time of inclusion of the patient in the study, after which the patient has been informed and has accepted to participate by signing the consent form. Follow-up visits will be performed after usual consultation, estimated at about every 3 months. No visit or additional examination will be requested by the protocol: modalities for follow-up and treatment will be left up to the entire judgement of the participating doctor. Data will be recorded during the 3 years of the patient's participation, except in case of withdrawal of consent, death of a patient or termination of the study before its planned end.

Total duration of the study is estimated at 7 years with an inclusion period of 4 years and a follow-up period of 3 years (see Figure 1). Throughout the study, at least one monitoring visit per year will be performed.

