### 9.2.1. Criteria for inclusion

Patients must satisfy all of the following criteria for inclusion in order to be eligible.

- Male or female patient 18 years of age or older;
- Patient with BCR-ABL Philadelphia chromosome positive or negative CML, in chronic, accelerated or blast phase;
- Patient resistant or intolerant to previous therapy with TKI for CP, AP or CB CML other than bosutinib;
- Patient initiating treatment with bosutinib for treatment of CP, AP or BP phase Ph+ / - CML at the end of the inclusion visit or during the one month prior to it;
- Patient who has been informed that a method of contraception must be used if a risk of pregnancy exists.
- Patients who have been informed about the study and who signed the informed consent form.

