### 9.2.2. Criteria for non-inclusion

Patients who satisfy one of the following criteria will not be included in the study:

- Patient with chronic, accelerated or blast phase BCR-ABL Philadelphia chromosome negative CML;
- Patient recently diagnosed with CML and who has not received previous treatment with a TKI;
- Patient currently treated with a treatment other than bosutinib;
- Patient of childbearing potential not using a method of contraception;
- Patient treated in the setting of an interventional study for another disease (outside of follow-up period);
- Patient who refuses computer processing of his/her medical data.

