## **9.5. Study sample size**

Since the descriptive objective of this study does not involve the hypothesis of specific research, it is not necessary to calculate a minimum sample size population of participating

patients. Furthermore, since CML is a rare disease, a minimum number of patients is not expected.

Based on the number of monthly prescriptions of Bosulif® (sponsor data) and taking into account the future start-up of a competitive study, a total of one hundred (100) patients included in the study appears to be a reasonable objective. Participating doctors should include on average 5 patients in the study, with no distinction between phases of CML at inclusion.

However, it is shown that about one hundred patients would make it possible to have acceptable precision, precision corresponding to half of a 95% confidence interval (CI):

- $\leq 10\%$  to estimate a percent of patients presenting with a given event (Wald asymptotic method without a continuity correction – hypothesis of a 50% rate)
- Of 10% in order to estimate median survival (Greenwood formula under the hypothesis of absence of data censored at the right before median survival and occurrence of a single event at a time).

Consecutive inclusion of patients who satisfy eligibility criteria up to the end of the inclusion period estimated at 2 years will ensure the representativeness of patients in the study.

In order to ensure compliance with this consecutiveness, a registry of non-inclusion will be set up. Patients eligible but not included in the study must be recorded in this registry and throughout the period of inclusion. A minimum of parameters will be collected.

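### The trial-participation exclusion names only studies of another disease, so a patient who starts bosutinib inside an interventional CML study remains eligible for a study of real-life use

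*Protocol*

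**What the plan says.** Protocol 9.2.2 has one criterion on participation in other research: "Patient treated in the setting of an interventional study for another disease (outside of follow-up period". The synopsis carries the same wording. I read the bracket as exempting patients who are only in the follow-up period of such a study.

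Two neighbouring criteria matter. Section 9.2.2 also bars a "Patient currently treated with a treatment other than bosutinib". Section 9.2.1 requires a "Patient initiating treatment with bosutinib for treatment of CP, AP or BP phase" CML, starting at the end of the inclusion visit or in the month before it. No criterion requires that bosutinib be prescribed as part of routine care.

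The design text assumes routine care. Section 7.4 says "This study will make it possible to obtain data on the real-life conditions of use of bosutinib", section 8.1 frames both primary objectives in the same terms, and section 9.1 says that "modalities for follow-up and treatment will be left up to the entire judgement of the participating doctor". Section 10.4 adds that products are used as usual, with no extra diagnostic or monitoring procedure.

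**The concern.** The eligibility rule and the design premise do not match. A patient who receives bosutinib under an interventional CML protocol may have dose changes, stopping and tests decided by that protocol rather than by the treating doctor. Those decisions feed directly into what this study measures: the percentage with related adverse events and the percentage stopping permanently after one (8.1, 9.7.2). They also feed into dose changes, interruptions, treatment duration, adherence and time to response (9.7.3).

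The criteria carry weight because sites are told to apply them exhaustively. Section 9.9.2 asks doctors to enrol every eligible patient in sequence, and sections 9.2 and 9.4.1.7 send eligible patients who are not enrolled to the non-inclusion registry. A site that left out a patient taking bosutinib in a CML trial would, on the wording, be leaving out an eligible patient.

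Any resulting distortion would be bias, so more patients would not reduce it.

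**Working it through.** **1. The plan's own figure.** Section 9.5 gives a 95% CI half-width of at most 10% for about 100 patients at a 50% rate, by the "Wald asymptotic method without a continuity correction". Check: 1.96 × √(0.5 × 0.5 / 100) = 0.098, or 9.8 points. The figure reproduces. It serves here only as a yardstick.

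**2. The criteria applied to four kinds of patient**, each otherwise eligible:

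- In the treatment phase of an interventional study of another disease: excluded by the trial-participation criterion.
- Only in the follow-up period of such a study: admitted by the bracketed exemption.
- In an interventional CML study and receiving a CML drug other than bosutinib: excluded by the criterion on other treatments, and not starting bosutinib as 9.2.1 requires.
- In an interventional CML study and starting bosutinib there: meets 9.2.1, is not on another treatment, and is not in a study of another disease. Nothing in 9.2.1, 9.2.2 or the synopsis excludes this patient.

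The gap is therefore the fourth group only.

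**3. The fourth group against the design text.** Sections 9.1 and 10.4 describe treatment and monitoring as the participating doctor's usual practice. A patient managed under another study's protocol need not fit that description. These sections describe the design and are not eligibility rules, so they show the intention without enforcing it.

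**4. Size.** The documents give neither the number of such patients nor how their event percentage would differ. Let f be their share and d the difference from routine-care patients. With routine-care percentage p, the overall percentage is (1 − f) × p + f × (p + d) = p + f × d, so the shift is f × d, in either direction. Taking d = 10 points purely as an assumption:

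- f = 5%: 0.05 × 10 = 0.5 points
- f = 10%: 0.10 × 10 = 1.0 point
- f = 20%: 0.20 × 10 = 2.0 points
- f = 30%: 0.30 × 10 = 3.0 points
- f = 0: no shift

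All of these lie below the 9.8-point half-width. A larger d would scale the shift in proportion, and nothing in the protocol selects a value of f or d.

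**5. Timing.** Data collection began on 22 October 2015 (section 6) and 9.1 gives a 4-year inclusion period, which ends about October 2019. This version is dated 15 February 2019, so about eight months of some 48 remained. A rewording alone would miss most of the enrolled patients.

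**The case against.** The strongest reply is that the protocol plainly intends routine care. Besides 9.1 and 10.4, section 9.10 has the medicinal products reimbursed by social security, and set-up and yearly monitoring visits (9.8.1, 9.8.2) check that sites understand the protocol. The text is also visibly a translation, so the limiting phrase may be a drafting slip rather than a decision to admit CML-trial patients. This part stands. It means that a site could enrol such a patient, not that it would. It does not close the gap, because the written criteria are what sites apply.

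Three stronger readings are tempting, and the documents do not support them.

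- A reader might infer that anyone in an interventional CML study is eligible. The criterion on other treatments already removes those on other drugs.
- A reader might take the remark in 9.5 about "taking into account the future start-up of a competitive study" as evidence that dual enrolment was expected. The protocol states neither the disease nor the type of that study, and the remark supports the target of 100. It reads most naturally as a study that would draw patients away.
- A reader might conclude that dual enrolment could never be detected. Section 9.3 lists no such variable, but it lists categories of data. The case report form is a separate document (Annex 1) that is not at hand, and sections 9.6.2 and 9.8.3 keep patients linkable to hospital records.

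It is also fair to say that a with-and-without presentation is analysis-plan detail. Who may enter the study is not: the protocol fixes that here.

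**Conclusion.** The point holds in a narrow form. As worded in 9.2.2 and the synopsis, the criteria admit a patient who starts bosutinib inside an interventional CML study, and this is at odds with the real-life premise of 7.4, 8.1, 9.1 and 10.4. The conclusion rests on the wording alone, and on reading the criterion on other treatments as meaning other CML treatments.

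The effect on the primary percentages cannot be derived from the protocol and may be zero. The 0.5 to 3.0 point illustration depends wholly on the assumed shares and the assumed 10-point difference and is no estimate of actual bias. The change is worth making because it is cheap and bears on the study's central claim; no distortion has been shown.

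**What to change.** In 9.2.2 and in the synopsis, widen the criterion to exclude patients treated in any interventional study, whether for CML or for another disease, and keep the existing follow-up-period exemption.

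Because recruitment was well advanced under this version, also record for patients already enrolled whether they were taking part in an interventional CML study at the same time, from source records if needed. If any were, report the two primary percentages with and without them. If none were, say so, which settles the question.

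The cost is a few words in two lists, one extra data item and possibly the loss of a few patients. Sections 4 and 9.5 state that no minimum number is expected, so that loss is tolerable.

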### 9.3. Variables

Patients will be identified indirectly via a unique number in the study (the centre no., patient no. pair).

The following “patient” data will be collected in the setting of the study at the usual consultation of patients in the centres.

Data	Role	Source
Compliance with criteria for inclusion and non-inclusion	Baseline characteristics	Inclusion visit
Demographic characteristics (year of birth, gender, weight, height, ECOG performance status)	Baseline characteristics	Inclusion visit
Diagnosis of CML (date of diagnosis, phase of CML at time of diagnosis, tests performed for diagnosis)	Baseline characteristics	Inclusion visit
Transcription of BCR-ABL gene at time of diagnosis	Baseline characteristics	Inclusion visit
Previous treatments of CML (type, dose, dosage, duration of previous treatment)	Baseline characteristics	Inclusion visit
Best response to previous treatments	Baseline characteristics	Inclusion visit
Reasons for change of previous treatments (if discontinuation for toxicity, description of the AE: type and grade)	Baseline characteristics	Inclusion visit
Phase of CML in the estimate of the participating doctor, at time of initiation of treatment with bosutinib	Baseline characteristics	Inclusion visit Follow-up visit
Evolution of mutational profile of BCR-ABL gene at time of initiation of treatment with bosutinib	Baseline characteristics	Inclusion visit Follow-up visit
Concomitant treatments at time of inclusion in the setting of management of CML	Baseline characteristics	Inclusion visit
Biological and hematological assessment data	Baseline characteristics Evaluation end point	Inclusion visit Follow-up visit
Hematological, cytogenetic and molecular response at time of inclusion and results	Baseline characteristics	Inclusion visit
Description of initiation of treatment with bosutinib (date of initiation, dose, dosage)	Baseline characteristics	Inclusion visit
Change to concomitant treatments in the setting of management of CML	Evaluation end point	Inclusion visit Follow-up visit
Description of treatment with bosutinib (changes to dose or dosage, temporary or permanent discontinuations of treatment)	Evaluation end point	Follow-up visit
Safety in treatment with bosutinib	Evaluation end point	Follow-up visit
Management of toxicities related to bosutinib (concomitant treatments, additional corrective medical measures)	Evaluation end point	Follow-up visit
Hematologic, cytogenetic and molecular tests performed for monitoring of response to treatment (type and frequency of monitoring, results of tests)	Evaluation end point	Follow-up visit
Compliance with treatment with bosutinib (Morisky Questionnaire) *	Evaluation end point	Follow-up visit
Quality of life (FACT-leu_v4)*	Baseline characteristics Evaluation end point	Inclusion visit Follow-up visit
Patient status and date of last news (date of death if applicable)	Evaluation end point	End of study
Last hematological, cytogenetic and molecular responses known	Evaluation end point	End of study

Status of treatment with bosutinib	Evaluation end point	End of study
------------------------------------	----------------------	--------------

\* Morisky medication adherence scale and fact leu self-questionnaire are intended solely for patients under treatment with bosutinib.

#### 9.4. Sources of data

A case report form (CRF) will be used for recording data. In the setting of this protocol, the CRFs are the reference for collection of medical data in electronic format or in paper format. Data will be collected according to two methods:

- By doctors in an electronic case report form (eCRF),
- By patients in paper format questionnaires.

Questionnaires collected at the different times of measurement are:

- At time of inclusion of patients: a questionnaire at inclusion completed by the doctors; questionnaires on compliance and quality of life completed by patients
- During follow-up of patients: a questionnaire on follow-up completed by the doctor; questionnaires on compliance and quality of life completed by patients
- In case of a premature end of study: end of study questionnaire completed by the doctor for patients lost to follow-up and/or withdrawal of consent.

##### 9.4.1. Patient data

Social and medical data collected will be obtained from patients' medical dossiers at follow-up visits usually performed in centres in the setting of routine management of the patient, estimated at every 3 months in the setting of evaluation of response to treatment.

Patients will also be asked to complete questionnaires on measurement of compliance with treatment, the Morisky medication adherence scale (completed at all follow-up visits, estimated at every 3 months) and measurement of quality of life, the FACT-leu questionnaire version 4 (completed only at visits corresponding to months *M0, M3, M6, M12, M18, M24 and M36*) in paper format, that they will complete on site and will return to the doctors at the corresponding visit.

Morisky and Fact LEU questionnaires will be completed only if the patient is under treatment with bosutinib. They will no longer be completed in long-term follow-up visits.

**Table 4 – Estimated schedule of data collection**

Estimated visits:	M0	M3	M6	M9	M12	M15	M18	M21	M24	M27	M30	M33	M36
Visits completed by the doctor (eCRF)													
Inclusion	x												

visit													
Follow-up visit		X	x	x	x	X	x	x	x	x	x	X	x
Self-questionnaires completed by patients (paper)													
Compliance (Morisky)		X	x	x	x	x	x	x	x	x	x	X	x
Quality of life (FACT-leu)	x	X	x		x		x		x				x

#### 9.4.1.1. Inclusion visit

Patients included will undergo collection of medical data indirectly by name (patients' questionnaires completed by the doctor *via* the eCRF).

#### 9.4.1.2. Follow-up visit

At each follow-up visit, conducted in the setting of usual management estimated every 3 months in conformity with recommendations on management of CML, doctors will complete *via* the eCRF a follow-up visit for all patients.

#### 9.4.1.3. Long-term follow-up visit

Patients who have permanently discontinued their treatment with bosutinib will be followed according to their usual management, estimated at every 3 months in conformity with recommendations of management of CML. Doctors will complete *via* eCRF a long-term follow-up visit for all these patients.

At this visit, the following information will be provided:

- Outcome of the CML Phase
- Therapeutic management of CML

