
NATURE AND DURATION OF STUDY
	
This is a national, observational, descriptive, prospective, multi-centre study conducted in Metropolitan France in adult patients treated for chronic phase, accelerated or blast phase Philadelphia chromosome positive (Ph+/-) CML, previously treated with one or more TKIs and for whom imatinib, dasatinib or nilotinib are not considered as appropriate treatments. The study will be conducted in all centres involved in management of CML, i.e. about twenty (20) centres are expected.
 
The study will be offered to all patients who satisfy criteria for eligibility up to the end of the recruitment period. Eligible patients but not included in the study will be recorded in a non-inclusion registry.
 
Patients will be followed prospectively throughout the duration of the study (3-year follow-up) starting from their inclusion in the study. Follow-up data will be collected at follow-up visits conducted in the setting of usual management, estimated at every 3 months independently of discontinuations, changes or discontinuations of treatment possibly implemented. Therapeutic management of the patient will not be

	
changed by participation in the study.

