#### 9.4.1.4. End of study questionnaire

An end of study visit will be completed by the participating doctor for all patients who discontinued the study before 36 months follow-up planned by the protocol (patient lost to follow-up, patient died or patient who withdrew their consent).

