**Median duration of response**

For each response (hematological, cytogenetic, molecular), the median duration of response will correspond to the median duration between first date of response as defined in the aforementioned and the confirmed loss of response, the progression of disease or death of the patient (Kaplan Meier method).

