**Progression**

Defined as passage from the chronic phase to the accelerated phase or to blast phase. This progression must be validated by two consecutive evaluations less than one week apart. Patients presenting an increase in leukocyte count in at least one period greater than or equal to one month, with second assay measurement  $> 20 \times 10^9/L$  and confirmed at least one week later. Patients presenting a loss of major hematological response (with hematological confirmation within a time greater than or equal to 2 weeks after loss of initial response) or non-confirmation of major cytogenetic response (with a Ph+ rate increased by 30%).

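### After bosutinib is stopped, the data listed for collection do not match the progression and loss-of-response definitions that PFS and response duration still use

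*Protocol*

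**What the plan says.** **After discontinuation.** Section 9.4.1.3 of the protocol gives patients off drug their own visit: "Patients who have permanently discontinued their treatment with bosutinib will be followed according to their usual management", about every 3 months. The information listed for that visit is "Outcome of the CML Phase" and "Therapeutic management of CML". Blood counts, cytogenetics, BCR-ABL and declared loss of response are not listed.

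**The ordinary visit.** Section 9.4.1.2 says that "doctors will complete *via* the eCRF a follow-up visit for all patients" and states no on-treatment limit. The table in section 9.3 places blood data and the hematological, cytogenetic and molecular tests at the follow-up visit.

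**End of study.** The same table asks for last known responses and vital status at end of study, but section 9.4.1.4 requires that form "for all patients who discontinued the study before 36 months follow-up planned by the protocol".

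**Endpoints (section 9.7.3).** PFS at 1, 2 and 3 years runs from bosutinib start to doctor-estimated progression or death. Progression covers phase change, a leukocyte rise, a hematological criterion ("Patients presenting a loss of major hematological response") and a cytogenetic criterion. Response duration ends at "the confirmed loss of response, the progression of disease or death of the patient". Neither endpoint is limited to time on bosutinib. The Synopsis has follow-up data collected "independently of discontinuations, changes or discontinuations of treatment possibly implemented".

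**The concern.** The endpoints need information that the off-drug visit does not list. A patient who stops bosutinib for intolerance, later loses response, and reaches M36 still in chronic phase may leave no dated record of that loss. From the stop onward, only phase change and death are sure to be recorded, so the curve would mix two event definitions that switch at discontinuation.

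An analysis plan can choose a censoring rule, but it cannot recover results that were never entered. The affected endpoints are secondary. The patients concerned are nonetheless central to the study, since permanent discontinuation after a bosutinib-related adverse event is a primary objective (section 8.1).

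**Working it through.** **1. Definitions against the off-drug list**

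| Event needed in section 9.7.3 | Listed in 9.4.1.3? |
|---|---|
| Progression: phase change | Yes |
| Progression: leukocyte rise | No |
| Progression: loss of major hematological response | No |
| Progression: cytogenetic criterion | No |
| Loss of hematological, cytogenetic or molecular response | No |

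One of four progression components is listed, and none of the three kinds of response loss. Death before 36 months is captured on the end-of-study form.

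**2. The plan's own precision figure.** Section 9.5 states a half-width of at most 10% with about 100 patients at a 50% rate. Check: 1.96 × √(0.25/100) = 9.8 points. It reproduces, and it is the yardstick for what follows.

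**3. Bias in 3-year PFS if patients stay at risk after stopping.** The protocol gives no figure for this, so the following is an illustration. Inputs:

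- True 3-year PFS S = 60% or 70% (assumed).
- Share off drug by 36 months d = 20% or 50%. The 20% is the share stopping bosutinib after an AE in study 200 (section 7.3). It is a low case because it counts AE stops only. The 50% is an assumption drawn from the 52% who stopped second-line dasatinib or nilotinib (section 7.2), which are other drugs.
- Share of events still visible after stopping q = 20% to 50% (assumed).
- Constant hazards, stopping independent of progression, and the same progression hazard on and off drug (assumed).

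With T = 36 months, λp = −ln(S)/T and λs = −ln(1−d)/T:

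S_obs = exp(−(λp+λs)T) + ∫₀ᵀ λs·exp(−(λp+λs)t)·exp(−q·λp·(T−t)) dt

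The integral equals λs·exp(−qλpT)·(1−exp(−kT))/k, with k = λs + (1−q)λp.

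Worked case, S = 0.60, d = 0.50, q = 0.20: λp = 0.01419, λs = 0.01925, k = 0.0306. The first term is 0.60 × 0.50 = 0.300. The second is 0.01925 × 0.903 × 0.668/0.0306 = 0.379. S_obs = 0.679, which is 7.9 points too high.

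| d | S | S_obs at q = 0.5 | S_obs at q = 0.2 | Overstatement (points) |
|---|---|---|---|---|
| 20% | 60% | 61.7% | 62.9% | 1.7 to 2.9 |
| 20% | 70% | 71.4% | 72.3% | 1.4 to 2.3 |
| 50% | 60% | 64.7% | 67.9% | 4.7 to 7.9 |
| 50% | 70% | 73.7% | 76.2% | 3.7 to 6.2 |

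**4. Bias if patients are instead censored at stopping.** Suppose the estimate is 60% and the off-drug hazard is r times the on-drug hazard. The value for the whole cohort then has exp(−r·λp·(T−t)) in place of the last factor in the integral, with λp from the 60%. Estimate minus true value, in points:

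| d | r = 0.5 | r = 1 | r = 2 |
|---|---|---|---|
| 20% | −1.7 | 0 | +2.7 |
| 52% | −4.9 | 0 | +7.5 |

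So the sign depends on r, which the protocol does not give.

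**The case against.** The strongest reply is that section 9.4.1.2 already requires the follow-up form for every patient. The restriction to patients on bosutinib in section 9.3 applies only to the two questionnaires, the schedule in Table 4 has no separate long-term row, and section 9.4.1.3 does not say that its two items are the only ones. The case report forms are a separate document and are not at hand. A reader might infer that these events cannot be seen after stopping. The documents do not establish that, and PFS uses the doctor's own date of progression. What remains is a conflict: section 9.4.1.3 is the specific rule for patients off drug, section 9.4.1 treats long-term visits as distinct, and sites could reasonably enter different data.

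A reader might also infer that PFS and response duration are certainly overstated. That needs patients to remain at risk after stopping. The PFS definition reads that way, but no censoring rule is stated, and the analysis plan may set one. Response duration could likewise be censored at the last response assessment.

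Nor does the bias fall mainly on those who did worst on the drug. A patient who stops because of progression or loss of response has that event at or before the stop, while the full form applies. For the same reason the 50% case is on the high side: its source includes stops for resistance.

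Finally, the Synopsis promises continued follow-up after discontinuation, not identical data.

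**Conclusion.** The mismatch is real and should be corrected. The long-term visit lists one of the four progression components and no loss of response, section 9.4.1.2 points the other way, and the end-of-study form does not cover patients who complete 36 months.

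If patients stay at risk after stopping, 3-year PFS and response duration are biased upward, mainly through those who stop for reasons other than failure, such as intolerance. For PFS the size is about 1.4 to 2.9 points with 20% off drug and about 4 to 8 points with 50%, against a stated precision of about 10 points. These figures rest on the assumptions listed above. No size was derived for response duration. If patients are censored at stopping, the bias may be upward, nil or downward. The documents support neither a claim that the events are certainly lost nor a claim of certain overstatement.

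**What to change.** Reconcile sections 9.4.1.2, 9.4.1.3 and 9.4.1.4 so that it is clear which form each patient has after stopping bosutinib and at M36.

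Add to the long-term follow-up page:

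- the dates and results of blood count, cytogenetic and BCR-ABL tests already done in routine care;
- doctor-declared progression or loss of response, with its date.

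The cost is some extra data entry at sites on an existing page. No visit or test is added.

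If the form is not changed, report two endpoints: phase transformation or death over 36 months, and full-definition progression and loss of response as a separate on-treatment endpoint. This costs no new data, but it gives up the full-definition PFS over 3 years.
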